Interestingly, 39% of the patients surveyed with the DPTQ reported linking the social aspect of HD. Based on these results, we performed a three-year longitudinal, prospective observational study on the formation of social networks in a new HD clinic and examined the networks' effects on kidney transplantation¹. Forty six racially and ethnically diverse patients (24% White, 33 % Black, 30% Hispanic, and 13% Multiethnic) were enrolled and studied with repeated survey measures and clinical observations. Thirty one patients (67%) were observed interacting with each other and participating in the HD social network (Appendix, Figure2). Gender, not race, was associated with participation in the social network. Almost all (91%) transplant eligible males were linked to other patients compared to 56.3% of the eligible women ($p=0.02$). Patients participating in the social network completed a median of 50% (Interquartile Range (IQR) 33 – 96%) of steps towards transplant compared to a median of 0% (IQR 0 – 23%) of those who did not ($p<0.001$). On sub-network analysis, patients who participated in health discussions with other patients, as well as those who received a kidney transplant had dense, sub-networks with higher clustering coefficients with the a mean of 50% of the patients in their network being interconnected with each other (0.52 ± 0.35 vs. 0.14 ± 0.30 , $p=0.0002$). Women, who participated in the social network, discussed their health more than men (90% vs 45% $p=0.02$) and tended to have a higher clustering coefficient (0.623 vs 0.356 , $p=0.07$). On further sub-network analysis, the percent of the work-up completed by a patient correlated with the steps completed by members of their sub-network ($R^2 = 0.42$, $p = 0.02$) and for patients who were interested but had not started the transplant process (step 2, Table 4), the clustering coefficients predicted the percentage of transplant steps completed ($\beta=2.23$; [95% CI], 0.16-4.29, $p = 0.003$, $r^2=0.19$). Lastly patients, who received a kidney transplant during the study had denser networks (0.71 ± 0.36 vs. 0.23 ± 0.32 , $p= 0.002$). These dense, highly connected networks as measured by the

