Analysis: We will compare and contrast both network and nodal attributes based on sex and race/ethnicity. We will use a multivariable linear regression to test if gender and race can predict clustering coefficient while controlling for age, HD vintage and socioeconomic status. We will refine our network model by adding and removing links with each wave of the survey. For the nodal attributes that are continuous variables, standard tests of hypothesis such as t-test, ANOVA, and linear regression will be used. For categorical attributes, ANOVA density-models as well as logistic regression models will be used. For continuous variables, testing distances and similarities, Moran statistics will be calculated. Since the observations are not independent observations drawn at random from a large population, we will use a boot-strap approach for estimating the variation of estimates from a large number of random sub-samples of network members⁵⁰⁻⁵².

Limitations: Having patients self-report their own social links, while an established methodology, can still be subject to recall bias⁵¹. Thus, we will use observations of social interactions for verification using the aforementioned log. These observations will be used to weight the survey generated links.

Approach to AIM 2: Using network information from AIM 1, we will examine how structural differences in social networks affect knowledge, attitudes, and behaviors towards kidney transplantation. **H2:** Patients with dense HD social networks have similar attitudes (both positive and negative) about transplantation and completion of steps to kidney transplant as compared to patients diffuse networks.

Rationale: We have found the primary barrier to the transplant wait-list is the completion of the work-up^{1,4}. Previous research shows that patients in small dense networks share similar ideas⁴². This could either positively^{1,26} or negatively¹⁰ affect access and progress to kidney transplantation. We are using steps completed to measure progress to transplantation; a measure has been established for transplant disparity research to improve the granularity of the measurement and compare results across studies².

Step	Description
1	suitability for referral to transplant center
2	interest in transplantation
3	referral call to transplant center
4	first visit to transplant center
5	transplant center work-up
6	work-up complete
7	active on the list
8	successfully received a kidney transplant

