Analytic Plan AIM 2: To test **H2**, we will use the network information from Aim 1 to analyze correlation of knowledge, attitudes, and behaviors between members of the network (transplant discussions, living donor recruitment, and step in kidney transplant process) from the surveys and the EMR.

Primary Outcome: Correlation of 1) attitudes about transplantation and 2) step in transplant process

Independent Variables: Clustering coefficient and attributes of alters

Covariates: Age, Marital Status, HD vintage, insurance, transplant eligibility, HD clinic, network attributes

Analysis: We will examine how knowledge, attitudes, and completion of steps differ by network attributes. These differences will then be validated by using logistic regression modeling to predict patient's attitudes towards transplantation and step in the transplant work-up using demographic and survey variables. We will then add network attributes and quantify the improvement in the prediction model using tests for goodness of fit. To further validate the model we will perform an Exponential Random Graph Model (ERGM) with temporal attributes⁵³ in which the patients current transplant step is a function of patients baseline data and network attribute as well as their alters' baseline step, current step, and network attributes.

Limitations: We have previously found that patients are often incorrect about their listing status⁴, thus we will confirm the transplant status by contacting the listing institution. Using the steps completed will allow for the analysis of patients that are highly motivated who complete all their work-up but are discovered to have an absolute contraindication to transplantation. Since AIM 1 and 2 are observational, we will be unable to determine whether patients form small networks with like-minded individuals or whether over time everyone in a small network will reach a common belief through spread of information and behaviors⁵⁴. To test the spread of information and behaviors, in **AIM 3**, we will use a network targeted intervention.

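### The Aim 2 logistic and goodness-of-fit tests make no allowance for correlation between networked patients, so they are likely to favour network effects somewhat too often

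*SAP*

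**What the plan says.** The Aim 2 analysis (SAP, section 3.C, Analytic Plan AIM 2) starts from differences in knowledge, attitudes and steps by network attribute. It continues: "These differences will then be validated by using logistic regression modeling to predict patient's attitudes towards transplantation and step in the transplant work-up". The network contribution is then tested: "We will then add network attributes and quantify the improvement in the prediction model using tests for goodness of fit". The predictors are given as "Independent Variables: Clustering coefficient and attributes of alters". No method for correlated patients is attached to these models. HD clinic is among the Aim 2 covariates; HD shift, listed for Aims 1 and 3, is not.

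Two other provisions bear on the point.

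- Under Aim 1 only, the SAP says: "Since the observations are not independent observations drawn at random from a large population, we will use a boot-strap approach". That bootstrap draws random sub-samples of network members. Aim 2 neither repeats it nor refers to it.
- Later in the Aim 2 analysis: "To further validate the model we will perform an Exponential Random Graph Model (ERGM) with temporal attributes". This model uses alters' baseline and current steps.

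In the Preliminary Results (section 3.A), the SAP reports that "the percent of the work-up completed by a patient correlated with the steps completed by members of their sub-network", with R² = 0.42 and p = 0.02.

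**The concern.** A likelihood-based fit test counts each patient as a separate piece of evidence. That fails when the outcome and the predictor are both shared within groups. Here H2 itself supposes that members of dense networks resemble one another in attitudes and steps, and the preliminary data point the same way for steps. The predictor is shared too: the SAP's Significance section describes a dense sub-network as one whose members have high clustering coefficients.

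In that setting the standard errors for network attributes are too small and the gain in fit is overstated. Aim 2 could then report that network structure predicts step or attitude when it does not.

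**Working it through.** **Inputs from the documents**
- R² = 0.42, p = 0.02; 46 patients enrolled, 31 (67%) in the network (SAP, Preliminary Results). The number behind the R² is not given.
- Expected sample 280 × 0.90 = 252 (SAP, Recruitment Goals).
- Significance level 0.05 (Protocol, Study Procedure and Data Analysis, item vi). Two-sided is assumed.

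**Assumptions, because the documents give no figures**
- Sub-network size m = 4 as the base case.
- Predictor intraclass correlation ρx = 0.3–0.8, and 0 for reference.
- One third of patients unlinked (252 / 3 = 84), after the 33% unlinked in the earlier study.
- Equal correlation within groups, and an outcome split in two at the median.

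**1. The SAP's own figure.** r = √0.42 = 0.648. With t = r√((n−2)/(1−r²)), n = 12 gives t = 0.648 × √(10/0.58) = 2.69 and p = 0.023. At n = 13, p = 0.017; at n = 31, p is about 0.0001. The reported p therefore fits only about 12–13 observations. At n = 12 the 95% interval for r is about 0.12 to 0.89.

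**2. Conversion to an intraclass correlation.** If R² relates a patient to the mean of k alters, R² = kρ²/(1+(k−1)ρ). For k = 3, ρ = 0.54 (check: 3 × 0.291/2.08 = 0.42). After a median split, the correlation of the binary outcome is (2/π) × arcsin(0.54) = 0.36.

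**3. Approximate error rate.** DE = 1 + (2/3)(m−1)ρyρx, where 2/3 is the linked share. The type I error is 2(1 − Φ(1.96/√DE)). With m = 4 and ρy = 0.36:

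| ρx | DE | Type I error |
|---|---|---|
| 0 | 1.00 | 5.0% |
| 0.3 | 1.22 | 7.6% |
| 0.5 | 1.36 | 9.3% |
| 0.8 | 1.58 | 11.9% |

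Simulated logistic likelihood-ratio tests on the same set-up (252 patients, 84 unlinked, 3,000 runs) agree: about 8% at 0.3, 9% at 0.5 and 12–13% at 0.8.

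**4. Is ρx of 0.3–0.8 plausible?** Clustering coefficients computed on randomly generated connected groups (assumed structures) had an intraclass correlation of 0.86 when dense and diffuse groups were mixed. When all groups had the same density it was 0.53 (groups of 4) and 0.26 (groups of 6).

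**5. Sensitivity.**
- Sampling error in r: with all patients in groups of 4, DE = 1 + 3ρyρx and no dichotomisation, the lower limit r = 0.12 gives 5.8–7.1% over ρx = 0.3–0.8. The upper limit r = 0.89 gives 14–26%.
- Groups of 10, ρx = 0.5, one third unlinked: 16–22%.

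**6. Candidate remedies.**
- Resampling patients one by one did not clearly restore 5%: 8% against 9.3% for the ordinary test (m = 4, ρx = 0.5, only 300 runs).
- Standard errors clustered on sub-network gave about 5–7% for groups of 3–4.
- If groups merge into shift-sized clusters (12 of 14 patients, assumed), the ordinary test rejects 19–38%. Uncorrected clustered Wald tests still reject roughly 8–12%.

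**The case against.** The strongest reply is that within-network correlation is what Aim 2 sets out to measure. Its primary outcome is correlation between members, alters' attributes are predictors, and a temporal ERGM follows. On that reading the dependence is the target and the plan already has a model for it.

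Part of this stands. Similarity between members is an Aim 2 target, and a reader would be wrong to infer that the SAP overlooks dependence altogether. But whether the clustering coefficient predicts step or attitude is a separate question, and for that question the similarity is nuisance. The ERGM is a later validation and does not change the logistic or goodness-of-fit p-values. Conditioning on alters is no cure if their concurrent outcomes are used. Reciprocal pairs are then counted twice, and in simulation with fully independent patients the likelihood-ratio test rejected 16–19% of the time.

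The reply also stands against over-precision. A reader might take √0.42, about 0.65, as a demonstrated intraclass correlation and conclude that network effects will certainly be declared too often. The documents do not support that. The figure relates a patient to sub-network members, rests on about 12–13 observations, and concerns steps only; none is given for attitudes. Sub-network size and ρx are not stated, and at ρx = 0 there is no inflation.

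**Conclusion.** The omission is real: as written, the Aim 2 regression and fit tests treat patients as independent, contrary to the SAP's own statement under Aim 1. The tests are likely, not certain, to be anti-conservative for shared predictors such as the clustering coefficient. A reasonable working size is 8–13% rejection at a nominal 5%. It rests on groups of 4, one third unlinked, ρx of 0.3–0.8, and the imprecise R² taken at face value for a binary outcome.

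A reader might infer that this undermines the trial. It does not. Aim 2 is observational within a self-described pilot, the SAP already says it cannot separate selection from spread, and the Aim 3 comparison of Cluster with Central does not use these tests. The point should be fixed before analysis but is not critical.

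**What to change.** In the Aim 2 analysis text of the SAP:

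1. Define sub-network operationally before analysis. In the SAP's Figure 1 example, the dense and diffuse sub-networks lie within one connected network, so a connected group may be most of a shift.
2. State that all Aim 2 regression and model-improvement tests use standard errors clustered on whole sub-networks, or a bootstrap that resamples whole sub-networks. Carrying over the Aim 1 member-level bootstrap is not enough.
3. Add a small-sample correction (t reference or bias-reduced variance). If connected groups merge into few, shift-sized clusters, use a within-shift network permutation test instead.
4. Replace the ordinary likelihood-ratio or goodness-of-fit p-value with the matching robust or permutation test.
5. Add HD shift to the Aim 2 covariates, as in Aims 1 and 3.

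Out-of-sample prediction by leaving out one shift at a time is optional; with 12 shifts it is a matter of preference.

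The cost is a few sentences, a little more analysis work and wider intervals. No new data are needed.

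### Aim 2 names only unqualified logistic regression for the eight-level transplant step: specify an ordinal or full-scale model so that the step is not collapsed at an unstated cut

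*SAP*

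**What the plan says.** The SAP, Approach to AIM 2, lists eight ordered steps, from suitability for referral at step 1 to "successfully received a kidney transplant" at step 8. The Rationale justifies counting steps as "a measure has been established for transplant disparity research to improve the granularity of the measurement and compare results across studies".

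Analytic Plan AIM 2 gives the primary outcome as "Correlation of 1) attitudes about transplantation and 2) step in transplant process". Its Analysis paragraph sets out this sequence:

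1. Examine how knowledge, attitudes and completion of steps differ by network attributes.
2. "These differences will then be validated by using logistic regression modeling", described in full as "using logistic regression modeling to predict patient's attitudes towards transplantation and step in the transplant work-up using demographic and survey variables".
3. Add network attributes to that model and measure the gain with goodness-of-fit tests.
4. Fit an Exponential Random Graph Model (ERGM) with temporal attributes "in which the patients current transplant step is a function of patients baseline data and network attribute", together with the steps and attributes of the patient's alters.

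Nothing states whether the logistic model is binary, ordinal or multinomial, and no cut on the step scale is given. The protocol does not settle it: its Study Procedure and Data Analysis section names descriptive statistics, chi-square tests, t-tests and time series analysis, but no regression.

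Elsewhere the step is kept on a fuller scale. In Preliminary Results, "the clustering coefficients predicted the percentage of transplant steps completed", reported with a slope and an r². In Aim 3, changes in completion of steps are compared by t-test.

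**The concern.** Without a qualifier, logistic regression usually means a model for a yes/no outcome. The SAP's own usage points the same way: in the Aim 1 Analysis paragraph, continuous nodal attributes go to t-tests, ANOVA and linear regression, and categorical ones go to ANOVA density models and logistic regression. An analyst following Aim 2 could reasonably split the eight steps into two groups.

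Two things would then be at stake. First, a patient who moves several steps on the same side of the cut counts as unchanged, so the detail for which the measure was adopted is lost in this model. Second, eight levels allow seven cuts. With none named in advance, the answer on whether network attributes improve prediction could depend on a cut chosen after looking at the data.

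**Working it through.** **Plan's own figure.** There is none. The SAP gives no sample size or power for Aim 2; its Retention/Attrition paragraph only says that the study is powered for the stated mortality and transfer rates. What follows is an illustration.

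**Inputs from the SAP**
- Expected recruitment for Aims 1 and 2: 252. All Aim 1 participants are analysed in Aim 2.
- Attrition: 10% mortality plus 5% transfer, so 252 × 0.85 = 214.
- Prior association of clustering coefficient with percentage of steps completed: r² = 0.19, so r = √0.19 = 0.436.
- Prior association of a patient's steps with those of the sub-network: R² = 0.42, so r = 0.648.
- Significance level 0.05 (protocol), taken as two-sided.

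**Assumptions not in the documents.** Independent patients, no covariates, a normal predictor and a normal latent step scale. Half of r, 0.436 / 2 = 0.218, is taken as a cautious effect. The SAP does not give this as its Aim 2 effect.

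**Formula check.** For a full-scale outcome, power = Φ(atanh(r)·√(n − 3) − 1.96). A cut leaving share p on one side multiplies r by φ(z_p)/√(p(1 − p)), which is 0.798 at p = 50% and 0.700 at p = 20%. With r = 0.218, n = 214 and √211 = 14.53:
- Full scale: 0.2215 × 14.53 − 1.96 = 1.26, power 89.6%.
- 50% cut: r = 0.174, 0.1757 × 14.53 − 1.96 = 0.59, power 72.3%, a loss of 17.3 points.
- 20% cut: r = 0.153, 0.1538 × 14.53 − 1.96 = 0.27, power 60.8%, a loss of 28.8 points.

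The formula treats the uncut outcome as continuous, so it somewhat overstates the loss relative to eight discrete levels. The simulation below uses the eight levels.

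**Simulation, r = 0.218, n = 214, 3,000 data sets per cell.** Linear test on the eight steps against the logistic likelihood-ratio test:

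| Assumed spread of steps | Full scale | Share at or above cut | Binary logistic | Loss (points) |
|---|---|---|---|---|
| Even | 87.0% | 50% | 73.0% | 14.0 |
| Even | 87.0% | 25% | 66.3% | 20.7 |
| Bell-shaped | 88.0% | 47% | 72.5% | 15.4 |
| Bell-shaped | 88.0% | 27% | 67.6% | 20.3 |
| Weighted to low steps | 85.7% | 55% | 72.4% | 13.4 |
| Weighted to low steps | 85.7% | 28% | 67.8% | 18.0 |
| Low steps, 20% at step 7 or above | 86.4% | 20% | 61.9% | 24.5 |

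(Losses were taken before rounding.) The range is about 13 to 25 points while each side holds at least about 20%. Cuts leaving 15% down to 4% on one side lose about 34 to 58 points. A rank test, standing in for proportional odds, has 84–86% power, up to about 3 points below the linear test.

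**Sensitivity to the effect assumed (formula, cuts from 50% to 20%)**
- Full prior effect, r = 0.436, n = 214: loss under 1 point.
- r² halved, r = √0.095 = 0.308: loss 2.2 to 6.6 points at n = 252, and 4.2 to 10.7 at n = 214.
- Half the sub-network correlation, r = 0.324, n = 214: loss 2.8 to 8.0 points.

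**Quality of the anchor.** The r² of 0.19 comes from a subgroup: patients interested but not yet started. In a simple regression, the printed interval 0.16 to 4.29 with about 21 degrees of freedom implies a standard error of 4.13 / (2 × 2.08) = 0.99 and t = 2.23 / 0.99 = 2.25. Then r² = 2.25² / (2.25² + 21) = 0.19, which matches. So the subgroup held about 23 patients. That t gives p of about 0.036, not the printed 0.003. The anchor is imprecise.

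**The case against.** The strongest reply is that proportional-odds and multinomial models are logistic regression too. The SAP mentions no dichotomy, and the absence of a cut fits an ordinal model as well as it fits an unstated split. That stands: a reader might infer that the plan requires a yes/no cut, and the text does not say so. It does not remove the point, because an ordinal model is not named and the bare term is normally read as binary. A multinomial model would ignore the order. With the seven listed covariates at one term each, it would need 7 × 7 = 49 slopes plus 7 intercepts for about 214 patients.

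Second, the logistic model is one stage of Aim 2. The primary outcome is worded as a correlation, step differences are examined before the regression, and the ERGM uses the current step with no cut mentioned. This also stands. A reader might infer that Aim 2 as a whole throws away the step scale, but the exposure is confined to the validation model and the test of added network attributes.

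Third, the size depends heavily on the assumptions. The SAP speaks of detecting half an effect only for COACH knowledge in Aim 3, so halving r here is a choice made for illustration. The SAP's own Aim 1 Analysis says network observations are not independent. Aim 3 tests change in steps between arms, a different quantity, and no document promises that its results will match Aim 2. All of this is accepted, so no single power figure should be quoted as the cost.

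**Conclusion.** The point holds in limited form. The model form for an eight-level primary-outcome variable is not specified, and the most ordinary reading of the wording would collapse it at an unstated cut. A full-scale model is better and costs almost nothing, so this is a cheap improvement rather than an error that invalidates the aim.

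The size is conditional. If the model is binary, r is 0.218, n is 214, patients are independent and there are no covariates, the loss is roughly 13 to 25 points for cuts leaving at least about 20% on each side. It is negligible if the full prior effect holds, and larger for an extreme cut. Covariates and network dependence would be expected to lower absolute power under either model. The documents do not support a stronger statement that Aim 2 will lose a particular amount of power: the cut, the spread of steps and the effect are all unknown. The freedom to choose the cut after seeing the data does not depend on these assumptions; it needs only that the model be binary.

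**What to change.** In the Analysis paragraph of Analytic Plan AIM 2, replace the general reference to logistic regression for the step with one named full-scale model. This can be proportional-odds (ordinal) logistic regression on the eight steps, or linear regression on steps completed, in line with the prior study's analysis. Add the network attributes to that same model and compare fit with and without them. Keep binary logistic regression for items that are truly yes/no, such as whether a patient has asked someone to donate. If a split of the step scale is in fact intended, state the cut and the reason for it before the data are analysed.

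The cost is about one sentence. No new data are needed, and ordinal regression is available in SPSS, which the SAP already lists. The small downside is that the proportional-odds assumption has to be checked and the check reported.
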